| Exclusion criteria | 
(1) Patients not suitable for PCI; thrombolytic therapy administered before randomization; cardiogenic shock;
 
(2) Any anticoagulant (heparin/LMWH, fondaparinux, warfarin or bivalirudin) or tirofiban administered within 48 hours before randomization;
 
(3) Active or recent major bleeding or bleeding predisposition, including retinal or vitreous hemorrhage within one month, GI or urinary track hemorrhage within 3 months, intracranial hemorrhage within 6 months or cerebral infarction within 3 months;
 
(4) Patients at high risk of secondary bleeding, including active gastric ulcer, ulcerative colitis, intracranial aneurysm, etc.;
 
(5) Major surgery (including ophthalmologic operation or neurosurgery) within 1 month;
 
(6) Clinical syndrome suspicious for aortic dissection, pericarditis or endocarditis;
 
(7) Uncontrolled blood pressure (>180/110 mmHg);
 
(8) Known hemoglobin <10 g/dL or platelet count <100 × 10⁹/L;
 
(9) Aminotransferase level >3x the upper limit of normal;
 
(10) Severe renal insufficiency (eGFR<30 mL/min/1.73m²);
 
(11) History of heparin induced thrombocytopenia;
 
(12) Known allergy to study medications or device (heparin, bivalirudin, tirofiban, aspirin, clopidogrel, stainless steel, contrast medium or hirudin) or allergic constitution;
 
(13) Patient pregnant or lactating, or planned pregnant within 1 year;
 
(14) Study subjects with poor compliance judged by investigators or patient ever participated in another clinical trial and has not completed the follow-up to the primary endpoint.
 |
| Study timelines | 
Start of the study: August, 2012.
 
First patient enrolled: August, 2012
 
Last patient finished: December, 2013
 |
| Statistical method | All primary and major secondary endpoints will be analyzed both on an intent-to-treat basis (all patients analyzed as part of their assigned treatment group) and on a per protocol basis (patients analyzed as part of their assigned treatment group only if they actually received their assigned treatment). The primary statistical analyses will be by intent-to-treat. |
| Version/date | V1.03/2012-04-09 |

22

23

Table of Contents

| | |
|---|----|
| 1. Background | 7 |
| 2. Objectives | 8 |
| 3. Introduction of study drug | 8 |
| 3.1 Bivalirudin | 8 |
| 3.2 Heparin | 9 |
| 3.3 Tirofiban | 10 |
| 4. Previous clinical research | 11 |
| 5. Design, randomization and blinding | 13 |

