 - 295 • Patient suffered from severe complications which necessitated withdrawing
 - 296 study medications.
 - 297 • Major deviation of the study protocol.
 - 298 • Severe adverse event that threaten the patient’s health.

299

300 **6.4.3 Criteria for drop out**

301 All patients enrolled in the trial shall be retained until completion of follow-up.
302 Patients have the right to withdraw from the study at any time without penalty, and
303 would not lose any benefits. The reasons that patients drop out may include but are
304 not limited to:

- 305 • Severe adverse events causing termination of the study.
- 306 • Unexpected illness for which further treatment would be inappropriate.
- 307 • Lost to follow-up.
- 308 • Patient withdrew informed consent.
- 309 • Other reasons causing termination of the study.
- 310 • Poor patient compliance which might affect efficacy or safety.

311

312 If patients met the above criteria and stop participating in the study, the
313 “completion of study” page in their case reports should be completed. Investigators
314 must report to their respective ethics committees when and why patients stopped
315 participating in the study (according to the procedures specified in each test body). If
316 patient withdrawal was caused by an AE/SAE, clinical follow-up should be performed
317 until the AE/SAE is resolved or stabilized.

318

319 **7. Methods**

320 **7.1 Study medications:**

- 321 • Bivalirudin for injection : 250mg per ampoule, manufactured by Salubris

322 Pharmaceutical Co. Ltd, Shenzhen, China

323 ● Heparin Sodium injection: 100mg per ampule

324 ● Tirofiban hydrochloride Sodium Chloride Injection: 100mg per package

325

326 **7.2 Follow-up:**

327 Clinical follow-up will be performed at 30 days, 6 months and 12 months after
328 randomization.

329

330 **7.3 Treatment**

331 Patients enrolled will be randomly assigned to receive bivalirudin alone, heparin
332 alone or heparin plus tirofiban in a 1:1:1 ratio. Treatments for 3 arms are as follows:

333

334 **7.3.1 Bivalirudin alone arm:**

335 Bivalirudin is given before coronary angiography in the catheterization laboratory,
336 initialized with a bolus of 0.75 mg/kg followed by infusion of 1.75 mg/kg/hr during
337 the PCI procedure and for at least 30 minutes but no more than 4 hours after
338 procedure. Following this mandatory infusion, a reduced dose infusion (0.2 mg/kg/hr)
339 for up to 20 hours may be administered at physician discretion. An additional

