340 bivalirudin bolus of 0.3 mg/kg is given if the activated clotting time (ACT) five
341 minutes after the initial bolus (measured with the Hemotec assay) is <225 seconds.

342 **7.3.2 Heparin alone arm:**

343 A bolus dose (100 U/kg) of heparin is given before coronary angiography in the
344 catheterization laboratory. Additional heparin bolus (20U/kg) is administered if the
345 post-bolus ACT was <225 seconds.

346 **NOTE:** Provisional (bailout) tirofiban use is allowed in the bivalirudin and heparin
347 alone arms for no-reflow, slow flow, visible thrombus or other thrombotic
348 complications. According to Chinese experts consensus, intra-coronary tirofiban
349 should be initialized as 500-750µg, and can be repeated after every 3-5 min, with a
350 total dose no more than 1500-2250µg. Intravenous tirofiban administration should be
351 initialized with a bolus of 10µg/kg (within 3min) and followed by a 0.15µg/kg/min
352 infusion for 18-36 hours.

353 **7.3.3 Heparin plus tirofiban arm:**

354 Study medications are started before coronary angiography in the catheterization
355 laboratory. Heparin 60 U/kg and tirofiban 10 µg/kg boluses (administrated within 3
356 min) are given followed by a 0.15 µg/kg/min tirofiban infusion for 18-36 hours.
357 Additional heparin bolus (20U/kg) is administered if the post-bolus ACT was <200
358 seconds.

359 **7.3.4 Adjunctive medications during perioperative period**

360 ● Dual antiplatelet therapy shall be given before randomization:

361 (1) Aspirin: 300mg loading followed by 100mg/d maintenance dose definitely.

362 (2) Clopidogrel: 300mg or 600 mg loading followed by 75mg/d maintenance dose
363 for 12 months. If a maintenance dose of clopidogrel (75mg/d) was given for at least
364 5 days before randomization, loading dose can be omitted.

365 ● Anticoagulant agent: Anticoagulant agent (heparin, LMWH, etc.) post
366 procedure is not recommended other than in patients who are at high risk of
367 thrombosis. LMWH administration is at physician's discretion for patients
368 undergoing IABP or temporary pacemaker implantation.

369

370 **8. Endpoints**

371 **8.1 Primary endpoint**

372 Primary endpoint is net adverse clinical events (NACE) at 30 days. NACE is defined
373 as a composite of major adverse cardiac and cerebral events (MACCE, all-cause death,
374 re-infarction, ischemia-driven target vessel revascularization or stroke) and any
375 bleeding events.

376 **8.2 Secondary endpoints:**

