505 and on a per protocol basis (patients analyzed as part of their assigned treatment group
506 only if they actually received their assigned treatment). The primary statistical
507 analyses will be by intent-to-treat.

508 • **Intention-to-treat (ITT) set:** Patients who meet the study inclusion criteria, sign
509 the written informed consent and receive study medications after randomization
510 and have any assessment for the primary endpoint will be included in the ITT set.
511 ITT set will be used as baseline characteristics and endpoint analysis.

512 • **Per protocol (PP) set:** Patients with a successful procedure and complete
513 follow-up information will be included in the PP set.

514

515 **12.3 Statistical method**

516 Data will be analyzed using SPSS V19.0 software package. Two sided test with
517 alpha level of 0.05 will be used.

518 Baseline demographic and clinical variables will be summarized for each of the
519 treatment groups for the ITT set. All continuous variables will be summarized using
520 means, standard deviations, medians, interquartile ranges, minimums and maximum

521 values and two-sided 95% confidence intervals. Categorical variables will be
522 summarized using frequencies and percentages with two-sided exact 95% confidence
523 intervals. P-values comparing the two treatment groups will be presented for
524 descriptive purposes. Continuous data will be summarized using mean and standard
525 deviation and compared using Student's t-test or one-way ANOVA. Time-to-event data
526 were compared with the log-rank test.

527 Pre-specified subgroups for analysis include gender, age, type of AMI, heart
528 failure, diabetes, anemia, renal insufficiency, arterial access, multivessel disease,
529 history of cardiovascular events, high bleeding risk, and PCI for left anterior
530 descending coronary artery.

531

532 **13. Quality Control**

533 Sponsor shall appoint monitors to conduct systematic monitoring for the study in
534 accordance with GCP principles to ensure the study is carried out according to the
535 protocol and the case report form is identical with original data. The monitors should
536 also assess compliance corresponding to the regulations and protocol.

537 Investigators must ensure the integrity of the medical files. All study files will be
538 reviewed by the sponsor and monitors. Monitors should ensure the following: the

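### Section 12.2 gives two different membership rules for the per-protocol analysis, and one of them selects on results seen only after treatment

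*Protocol*

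**What the plan says.** The synopsis (Statistical method) and the lead paragraph of Section 12.2 give the same rule. On the per-protocol basis, patients are analysed in their assigned group "only if they actually received their assigned treatment". Both places apply this to all primary and major secondary endpoints, alongside ITT, and both state which basis leads: "The primary statistical analyses will be by intent-to-treat".

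The bullet that defines the PP set, a few lines later in Section 12.2, reads "Patients with a successful procedure and complete" and continues "follow-up information will be included in the PP set". It sets no condition on the treatment received.

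Three other places bear on the point:
- Section 7.3 starts study drug before coronary angiography. It allows bailout tirofiban in the bivalirudin and heparin "alone arms for no-reflow, slow flow, visible thrombus or other thrombotic" complications.
- Section 6.4.3 includes among the reasons for drop-out "Severe adverse events causing termination of the study".
- Appendix 1 defines the clinical endpoints but not procedural success.

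**The concern.** One analysis has two membership rules, and the text does not connect them. Someone building the PP set from the bullet and someone building it from the lead paragraph could produce different sets, and each could cite the protocol.

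The more serious problem is what the bullet selects on. A PP set is normally restricted by adherence. The bullet restricts by how the procedure went and whether follow-up was finished. Both are known only after randomisation and after study drug has been given, and an antithrombotic can influence both. If one arm has more failed procedures and those patients have more events, dropping them improves that arm's PP result. A reader who takes the PP analysis as support for ITT could then be misled, whether the two agree or differ.

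**Working it through.** **The two rules side by side**

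| Patient | Synopsis and lead paragraph | PP bullet alone | Both applied jointly |
|---|---|---|---|
| Assigned drug given, procedure unsuccessful | in | out | out |
| Assigned drug given, follow-up incomplete | in | out | out |
| Another arm's drug given, procedure successful, follow-up complete | out | in | out |
| Assigned drug given, procedure successful, follow-up complete | in | in | in |

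The first two rows leave the set under the joint reading too, so combining the rules does not remove the selection.

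**The terms in the bullet.** Procedural success has no definition, and Section 14 does not list it among the events judged by the blinded committee. Complete follow-up has no time point. Section 12 analyses the primary endpoint once all patients have reached 30 days. If complete means 12 months, the PP set cannot be known at that analysis. The text also does not say how a patient who dies counts.

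**The plan's own figure.** Section 12.1 claims more than 90% power with 700 per group, 5% lost to follow-up, two-sided alpha 0.05 and a 45% reduction. Evaluable per group: 700 × 0.95 = 665. Bivalirudin rates: 11.5% × 0.55 = 6.325% and 12.1% × 0.55 = 6.655%. A pooled two-proportion test gives 91.3% and 92.7%, so the claim reproduces. (A continuity correction gives 89.6% and 91.3%.) Nothing in this point changes these figures.

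**Possible size of the bias.** The documents give no failure rates by arm and no event risk after failure, so these inputs are assumed:
- overall NACE p = 11.5% in both arms (the plan's heparin-alone rate, with no true difference);
- failure f = 5% in control, and 8% or 10% in bivalirudin;
- NACE risk after failure q = 20%, 30% or 50%, the same in both arms.

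PP rate = (p − f × q) / (1 − f).

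| q | Control, f = 5% | Bivalirudin, f = 8% | RR | Bivalirudin, f = 10% | RR |
|---|---|---|---|---|---|
| 20% | 0.105/0.95 = 11.05% | 0.099/0.92 = 10.76% | 0.97 | 0.095/0.90 = 10.56% | 0.96 |
| 30% | 0.100/0.95 = 10.53% | 0.091/0.92 = 9.89% | 0.94 | 0.085/0.90 = 9.44% | 0.90 |
| 50% | 0.090/0.95 = 9.47% | 0.075/0.92 = 8.15% | 0.86 | 0.065/0.90 = 7.22% | 0.76 |

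Starting from 665 per arm, the chance of a nominally significant PP result favouring bivalirudin (2.5% if unbiased) is 3.6-4.6% at q = 20%, 5.6-9.2% at 30% and 13-30% at 50%. With f = 5% in both arms, the RR is 1.00 and the chance is 2.5%.

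The direction does not depend on holding the overall rates equal. Suppose instead that risk after success is 9.47% and after failure 50% in both arms, with failure in 5% of control and 10% of bivalirudin patients. The full-arm rates are then 11.5% and 0.10 × 0.50 + 0.90 × 0.0947 = 13.5%, a relative risk of 13.5/11.5 = 1.18. The PP relative risk is 1.00, so the PP set hides the difference.

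**The case against.** The strongest reply is that the two statements need not conflict. The lead paragraph's wording sets a necessary condition, and the bullet can be read as adding to it. A reader might infer that the rules are incompatible, that the bullet is the operative one, and that a patient given the wrong drug therefore enters the set. The documents do not support that much, because they name no governing rule and the joint reading is open. What stands is that the text does not say so, and that the joint reading keeps the selection on later results.

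A reader might also infer that patients with no-reflow are excluded, or that the set does remove failures unequally by arm. Neither is established. No-reflow appears as a reason for bailout tirofiban, not as a failed procedure, and no failure rates by arm are given. Unequal removal is possible, not shown.

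The consequence is limited too. This is a superiority trial with ITT primary, and the success rule in Section 12.1 does not refer to the PP set. In the table, the spurious difference runs from 0.3 to 2.3 percentage points, against a planned difference from heparin alone of 11.5 − 6.325 = 5.2 points.

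Finally, receipt of assigned treatment is itself known only after randomisation, so no PP set is free of selection. That is true, but it is less directly tied to outcome than procedural success is.

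**Conclusion.** The point holds in this form: the protocol gives two membership rules for one analysis without reconciling them, and the bullet selects on results that treatment may affect, whether it is applied alone or jointly. The PP comparison can be biased in favour of the arm with more procedural failures. Under the assumed inputs the relative risk with no true difference runs from 0.97 down to 0.76. That range requires failure rates that differ by arm and an event risk after failure above the overall rate; with equal failure rates and equal risk after failure there is no bias. If control had more failures, the tilt would go against bivalirudin.

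A reader might infer that the trial's primary conclusion is at risk. It is not on this ground: only the supportive PP analyses of the primary and major secondary endpoints are affected. Nor is this a detail that can be left to an SAP, because the protocol itself states both rules.

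**What to change.** Replace the PP bullet in Section 12.2 with the rule already in the synopsis and lead paragraph: ITT patients who were in fact given their assigned treatment. Delete the conditions on procedural success and complete follow-up. Add one sentence saying that a patient who dies or has a NACE event within 30 days has a known primary outcome.

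No further eligibility or deviation criteria are needed to cure the defect, and the synopsis and lead paragraph can stay as they are. The cost is a minor text change. Sample size and stated power are unaffected. The PP analysis remains supportive, since treatment received is still a post-randomisation condition.

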254 vitreous hemorrhage within one month, GI or urinary track hemorrhage within 3
255 months, intracranial hemorrhage within 6 months or cerebral infarction within 3
256 months;

257 (4) Patients at high risk of secondary bleeding, including active gastric ulcer,
258 ulcerative colitis, intracranial aneurysm, etc.;

259 (5) Major surgery (including ophthalmologic operation or neurosurgery) within 1
260 month;

261 (6) Clinical syndrome suspicious for aortic dissection, pericarditis or endocarditis;

262 (7) Uncontrolled blood pressure (>180/110 mmHg);

263 (8) Known hemoglobin <10 g/dL or platelet count <100 × 10⁹/L;

-
- 264 (9) Aminotransferase level >3x the upper limit of normal;
265 10) Severe renal insufficiency (eGFR<30 mL/min/1.73m²);
266 (11) History of heparin induced thrombocytopenia;
267 (12) Known allergy to study medications or device (heparin, bivalirudin, tirofiban,
268 aspirin, clopidogrel, stainless steel, contrast medium or hirudin) or allergic
269 constitution;
270 (13) Patient pregnant or lactating, or planned pregnant within 1 year;
271 (14) Study subjects with poor compliance judged by investigators or patient ever
272 participated in another clinical trial and has not completed the follow-up to the
273 primary endpoint.

274

275 **6.4 Criteria of patient removal, treatment discontinuation and drop out**

276 **6.4.1 Criteria of removal**

277 Patient should be removed if:

- 278 • Misdiagnosis.
- 279 • Without any record of physical or laboratory test results.
- 280 • Do not meet the inclusion criteria or meet at least one exclusion criteria.

281 The reason of removal should be written down and the case report form (CRF) should
282 be preserved for audit check. Removal patients will not be included in the efficacy
283 analysis but could be included in the safety analysis if there are any records regarding
284 efficacy or safety.

285 **6.4.2 Criteria of treatment discontinuation**

286 Discontinuation of any study medication is defined as stopping experimental
287 treatment. The reason of discontinuation should be clearly noted in the original
288 medical records and CRF.

289 Treatment should be discontinued if:

- 290 • Patient withdrawal of informed consent.
- 291 • Intolerable side effects of study medications

-
- 292 • Severe allergy that cannot be relieved by anti-allergic therapy
 - 293 • Adverse events or abnormal laboratory test results indicating that
 - 294 continuation of treatment would be inappropriate.

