377 ● NACE at 12 months;

378 ● MACCE at 30 days and 12 months;

379 ● Any bleeding events (evaluated by BARC classification) at 30 days and 12
380 months.

381 **8.3 Safety endpoints**

382 ● Stent thrombosis (definite or probable by ARC definition) at 30 days and 12
383 months;

[figure not shown]
- Thrombocytopenia at 30 days;
- Any other abnormal symptoms, signs or laboratory test results with clinical significant.

387

388

389 **9. Study flowchart:**

390 See Figure 1.

391

392

393

394

395

396

Figure 1. Study flowchart

397 **10. AE/SAE reporting**

398

399 There are two classifications of adverse events: adverse event (AE), and serious adverse
400 event (SAE). Adverse events must be monitored until resolved or adequately explained. All
401 serious and unanticipated adverse events must be reported, regardless of the cause. They
402 should be reported to the local IRB/EC and Sponsor within 24 hours of knowledge of the
403 event.

404 **10.1 Definition of AE / SAE**

405 ● **AE**

406 Any adverse medical events occurring in a clinical trial, not necessarily
407 having a causal relationship with the study treatments. Adverse events could be
408 any signs (including abnormal laboratory values), symptom, or temporary disease,
409 whether related or unrelated to the study drug use. An adverse event may be
410 categorized as the following:

- 411 • Mild – signs or symptoms that do not interfere with the patients’ usual
412 activities or is transient and resolves without treatment of sequelae.
- 413 • Moderate – interferes with the patients’ usual activities and/or requires
414 symptomatic treatment.
- 415 • Severe – symptoms causing severe discomfort and significant impact the
416 patient’s usual activities and requires treatment.

417 ● **SAE**

418 A study-related event that is fatal, life-threatening, requires inpatient
419 hospitalization or prolongation of an existing hospitalization, requires
420 intervention to prevent permanent impairment/damage, or results in persistent or
421 significant disability.

422

423 **10.2 Observation and recording of AEs**

424 Investigators should collect and record all AEs occurring from the time of signing
425 informed consent for each subject to end of the follow-up in the clinical study.

426 For AEs, only medical events with clinical worsening compared to baseline are
427 recorded. Abnormal evaluation results at screening or baseline examination are not

428 considered AEs.

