539 rights of the subjects should be protected; original data should comply with GCP and
540 protocol requirements.

541

542 **14. Clinical Event Committee (CEC)**

543 A Clinical Events Committee (CEC) is organized for this study. The committee is
544 composed of a number of interventional cardiologists who are not participations in
545 this study. The committee shoulders the mission for the classification of clinical
546 events and the development of specific criteria of clinical endpoints used in this study.
547 The CEC will request the original data as necessary. All CEC members are familiar
548 with the protocol of this study. All events are judged based on ARC, BARC and other
549 standard definitions (Appendix 1). The Committee shall regularly make assessments
550 and judgments on death, myocardial infarction, ischemia-driven target vessel
551 revascularization, stent thrombosis, bleeding, stroke and thrombocytopenia events

552 which occur during the trial.

553

554 **15. Ethics Committee**

555 Before study initiation, the study director must submit the study protocol, informed
556 consent form and other related study documents to the Ethics Committee to obtain its
557 approval for conducting the clinical trial. After receiving the application, the Ethics
558 Committee will convene a meeting to review, discuss and issue written comments
559 attached with the list of participants, professional information and signature of
560 primary investigator. During the study, the sponsor or contract research organization
561 appointed by the sponsor should promptly report serious adverse events, including
562 risks to subjects and other issues. Any modification to the protocol should be
563 approved and recorded by the Medical Ethics Committee.

564

565 **16. Study Management**

566 **16.1 Modification in the protocol**

567 Any modification in the protocol should be released by sponsor and signed by
568 investigators. The updated protocol should be saved as an annex. Any modification to
569 protocol should be approved and recorded by the Medical Ethics Committee.

570 If deviations from the protocol are necessary, investigators should inform the sponsor
571 as soon as possible, and discuss the specific situation to reach an agreement. The
572 reason for deviation from the protocol should be recorded.

573 If the telephone or address is changed during the study, the sponsor will inform
574 investigators in writing without modification to protocol.

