764 professional; may include episodes leading to self-discontinuation of medical therapy
765 by the patient without consulting a healthcare professional.

766 Type 2: any overt, actionable sign of hemorrhage (eg, more bleeding than would be
767 expected for a clinical circumstance, including bleeding found by imaging alone) that
768 does not fit the criteria for type 3, 4, or 5 but does meet at least one of the following

769 criteria: (1) requiring nonsurgical, medical intervention by a healthcare professional,
770 (2) leading to hospitalization or increased level of care, or (3) prompting evaluation.

771 Type 3:

772 Type 3a: Overt bleeding plus hemoglobin drop of 3 to <5 g/dL (provided hemoglobin
773 drop is related to bleed); any transfusion with overt bleeding.

774 Type 3b: Overt bleeding plus hemoglobin drop ≥ 5 g/dL (provided hemoglobin drop is
775 related to bleed); cardiac tamponade; bleeding requiring surgical intervention for
776 control (excluding dental/nasal/skin/hemorrhoid); Bleeding requiring intravenous
777 vasoactive agents.

778 Type 3c: Intracranial hemorrhage (does not include microbleeds or hemorrhagic
779 transformation, does include intraspinal); Subcategories confirmed by autopsy or
780 imaging or lumbar puncture; Intraocular bleed compromising vision.

781 Type 4: CABG-related bleeding: Perioperative intracranial bleeding within 48 h;
782 Reoperation after closure of sternotomy for the purpose of controlling bleeding;
783 Transfusion of ≥ 5 U whole blood or packed red blood cells within a 48-h period;
784 Chest tube output ≥ 2 L within a 24-h period.

785 Type 5: fatal bleeding.

786 Type 5a: Probable fatal bleeding; no autopsy or imaging confirmation but clinically
787 suspicious.

788 Type 5b: Definite fatal bleeding; overt bleeding or autopsy or imaging confirmation.

789

790 **Acquired thrombocytopenia.** Acquired thrombocytopenia is defined as a platelet
791 count decrease by >50% or by $>150 \times 10^9/L$ from baseline.

792

793

794

795

796

797

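### The fixed-fall limb of the thrombocytopenia definition adds only patients whose count stays above 150 x 10^9/L, and no limb captures a low count reached

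*Protocol*

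**What the plan says.** Appendix 1 (Definitions) gives acquired thrombocytopenia one sentence: a platelet "count decrease by >50% or by $>150 \times 10^9/L$ from baseline". The two limbs are joined by *or*, and both measure change from baseline. Nothing elsewhere in the protocol adds a level that the count must reach.

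The definition serves the safety endpoint "Thrombocytopenia at 30 days" (section 8.3 and the synopsis). Section 14 has the Clinical Events Committee judge events by the Appendix 1 definitions, and its list includes "revascularization, stent thrombosis, bleeding, stroke and thrombocytopenia events".

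The only absolute platelet level in the protocol is exclusion criterion 8 in section 6.3: "Known hemoglobin <10 g/dL or platelet count <100 × 10⁹/L". Table 1 schedules routine blood tests at baseline only.

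**The concern.** A percentage fall and a fixed fall joined by *or* cross over at one baseline value. Below it, one limb does no work. Here the crossover is at 300 x 10^9/L. The limb that takes over above it acts on patients who start high and still have a high count afterwards. Patients who start nearer the entry limit are judged by the 50% rule alone, so they can end below that limit and not be counted.

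Section 3.3.3 reports that platelet decreases were more likely with tirofiban plus heparin than with heparin alone, and section 3.1.3 lists thrombocytopenia among bivalirudin's rare reactions. A platelet comparison across the three arms is therefore of real interest. At stake is whether the events counted under this heading are the ones a reader would take the word to mean.

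**Working it through.** The protocol states no figure for this endpoint, so there is none to reproduce. The check is algebra on the definition.

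**Inputs** (counts in 10^9/L). B is the baseline count, N the later count and f = B − N the fall. From Appendix 1, limb 1 is f > B/2 and limb 2 is f > 150. From section 6.3, a known count below 100 is excluded at entry.

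**When limb 2 matters.** If B ≤ 300, then B/2 ≤ 150, so f > 150 implies f > B/2 and limb 2 is redundant. A case that meets limb 2 alone needs 150 < f ≤ B/2. That requires B > 300, and then N = B − f ≥ B/2 > 150. Every case that limb 2 adds therefore ends above 150.

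Enumerating whole-number counts for baselines 100 to 600 agrees. There is no limb-2-only case at B ≤ 300 and none with N ≤ 150. The smallest baseline with such a case is 302 (302 to 151).

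| Baseline | Limb 1 met if count is below (B/2) | Limb 2 met if count is below (B − 150) |
|---|---|---|
| 180 | 90 | 30 |
| 250 | 125 | 100 |
| 300 | 150 | 150 |
| 350 | 175 | 200 |
| 400 | 200 | 250 |
| 450 | 225 | 300 |

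**Low counts not captured.** At B ≤ 300 the event rule reduces to N < B/2. A patient ends below 100 without being an event when B/2 ≤ N < 100. At B = 180 that is 90 to 99. In whole numbers the band ends at B = 198, where 198 to 99 is a fall of exactly 50% and does not count. At B = 199 it is empty, because 199 to 99 is a fall of 100 (50.3%) and counts.

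**Single cases under the definition as written:**

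| From → to | Fall | % fall | Event? |
|---|---|---|---|
| 400 → 245 | 155 | 38.8 | Yes, limb 2 only |
| 450 → 299 | 151 | 33.6 | Yes, limb 2 only |
| 400 → 190 | 210 | 52.5 | Yes, both limbs |
| 250 → 130 | 120 | 48.0 | No |
| 180 → 95 | 85 | 47.2 | No |
| 160 → 85 | 75 | 46.9 | No |

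**How many patients limb 2 could touch.** The protocol gives no baseline platelet distribution. Under assumed normal distributions, the share with B > 300 is 2.3% (mean 200, SD 50), 9.1% (mean 220, SD 60) or 23.8% (mean 250, SD 70). This is the share exposed to limb 2, not the share reclassified by it.

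**The case against.** The best defence is that nothing here is contradictory. The definition is labelled *acquired* and measures a fall from baseline. Section 3.3.3 also speaks of decreases, which a fall-based endpoint measures directly. The limit of 100 is an eligibility criterion and is not stated as an event threshold, and the protocol gives no lower limit of normal. All of that is correct, and a relative fall is a legitimate choice. It supports the >50% limb. It does not explain a second limb that is inactive up to 300 and, above that, adds only patients who remain above 150.

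A reader might go further and infer that low counts go unrecorded. The protocol does not support that. Section 8.3 also lists other clinically significant laboratory abnormalities, and section 10.1 counts abnormal laboratory values among adverse events. A fall from 180 to 95 could be recorded in either place, though not under this endpoint.

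A reader might also infer that the comparison between arms is biased. That is not shown. One rule applies to all arms, the adjudicating committee is blinded, and no frequency of misclassification can be derived.

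Finally, a reader might conclude that 150 is a slip for a level reached. That is plausible, but the text reads as a fall in both limbs and the protocol cannot settle the intent.

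**Conclusion.** The point holds as a defect in one safety definition. The redundancy up to a baseline of 300 is exact and needs no outside figure. So is the result that every case added above 300 ends above 150. Calling those counts normal would need a lower limit that the protocol does not give, but they all lie above the protocol's own 100. As written, 450 to 299 is thrombocytopenia and 180 to 95 is not.

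Two limits apply. The missed band is narrower than all falls below 100: it runs only from half the baseline up to 100, for baselines of about 100 to 198. Limb 2 is also not the only source of events above 150, because the >50% limb produces some too (400 to 190).

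Thrombocytopenia is not a component of NACE or MACCE, so the primary endpoint, its hypothesis and the sample size are unaffected. The point should be corrected, but it does not threaten the trial's main conclusion.

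**What to change.** The sponsor should state whether 150 was meant as a fall or as a level reached. The second limb should then become an absolute nadir in patients at or above that level at baseline: below 150 x 10^9/L if that was the intent, or below the protocol's own 100 x 10^9/L. Keep the >50% fall as the other limb, and report the two limbs separately by arm.

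With either level, 400 to 245 and 450 to 299 stop being events, and 180 to 95 and 160 to 85 become events. The levels differ on 250 to 130, which counts at 150 and not at 100. They also differ for baselines of 100 to 149, where the 150 version leaves only the 50% rule: 130 to 70 (60/130 = 46.2%) would still not count.

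The text change is one sentence in Appendix 1, plus the committee's adjudication instructions. There are three downsides:

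- The >50% limb will still flag some counts above 150.
- A nadir limb will count small falls across the threshold.
- Because Table 1 schedules blood tests at baseline only, nadirs will rest on counts taken in routine care unless later counts are scheduled. Reports should say so.
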